# 14.3.9 Analysis of exploratory endpoints

The analysis of exploratory endpoints will be based on the FAS.

The analysis of exploratory endpoints will resemble the primary analysis for the primary estimand related to a specific endpoint type: binary, continuous, or time to event. For details refer to Section 14.3.6 (for binary endpoints refer to Section 14.3.6.2, for continuous endpoints refer to Section 14.3.6.3, and for time-to-event endpoints refer to Section 14.3.6.4).

Panel 25 provides an overview of the statistical analysis of the exploratory endpoints.

Panel 25: Overview of the statistical analysis of exploratory endpoints

Endpoints	Type of endpoint	Prima	ry estimand
		Strategy to handle IEs	Handling of missing data and data collected after IE
Efficacy			
IGA-CHE TS at Weeks 1, 2, and 12	Binary	Composite	Non-response imputation
HECSI-75 at Weeks 1, 2, 4, and 12	Binary	Composite	Non-response imputation
HECSI-90 at Weeks 1, 2, 4, 8, and 12	Binary	Composite	Non-response imputation
Percentage change in HECSI score from baseline to Weeks 1, 2, 4, 8, and 12	Continuous	Composite	WOCF (including baseline value)
Reduction of HESD itch score (weekly average) of ≥4 points from baseline at Weeks 1 and 12 	Binary	Composite	Non-response imputation
Reduction of HESD itch score (weekly average) of ≥3 points from baseline at Weeks 1, 2, 4, 8, 12, and 16 	Binary	Composite	Non-response imputation
Time to reduction of HESD itch score (weekly average) of ≥4 points 	Time to event	While on treatment	Not applicable
Change in HESD itch score (weekly average) from baseline to Weeks 1, 2, 4, 8, and 12	Continuous	Composite	WOCF (including baseline value)
Reduction of HESD score (weekly average) of ≥4 points from baseline at Weeks 1, 2, and 12 	Binary	Composite	Non-response imputation
Reduction of HESD score (weekly average) of ≥3 points from baseline at Weeks 1, 2, 4, 8, 12, and 16 	Binary	Composite	Non-response imputation

Trial ID: LP0133-1402 Date: 20-Aug-2021

Version: 4.0, Final Page 125 of 157

Endpoints	Type of endpoint	Prima	ary estimand
		Strategy to handle IEs	Handling of missing data and data collected after IE
Time to reduction of HESD score (weekly average) of ≥4 points 	Time to event	While on treatment	Not applicable
Change in HESD score (weekly average) from baseline to Weeks 1, 2, 4, 8, and 12	Continuous	Composite	WOCF (including baseline value)
Reduction of HESD pain score (weekly average) of ≥4 points from baseline at Weeks 1, 2, and 12 	Binary	Composite	Non-response imputation
Reduction of HESD pain score (weekly average) of ≥3 points from baseline at Weeks 1, 2, 4, 8, 12, and 16 	Binary	Composite	Non-response imputation
Time to reduction of HESD pain score (weekly average) of ≥4 points 	Time to event	While on treatment	Not applicable
Change in HESD pain score (weekly average) from baseline to Weeks 1, 2, 4, 8, and 12	Continuous	Composite	WOCF (including baseline value)
Change in HESD (weekly average for each individual symptom [excluding itch and pain]) score from baseline to Week 16	Continuous	Composite	WOCF (including baseline value)
Health-related quality of life and efficacy	1	•	-
Change in HEIS score from baseline to Weeks 1, 2, 4, 8, and 12	Continuous	Composite	WOCF (including baseline value)
Reduction of HEIS score of $\geq$ 1.5 points at Weeks 1, 2, 4, 8, 12, and 16 	Binary	Composite	Non-response imputation
Change in HEIS PDAL score from baseline to Weeks 1, 2, 4, 8, and 12	Continuous	Composite	WOCF (including baseline value)
Reduction of HEIS PDAL score of $\geq$ 1.5 points at Weeks 1, 2, 4, 8, 12, and $16^8$	Binary	Composite	Non-response imputation
Change in HEIS (each individual domain [excluding PDAL]) score from baseline to Weeks 1, 2, 4, 8, 12, and 16	Continuous	Composite	WOCF (including baseline value)
Reduction in DLQI score of ≥4 points at Weeks 1, 4, 8, and 12 	Binary	Composite	Non-response imputation
Change in DLQI score from baseline to Weeks 1, 4, 8, and 12	Continuous	Composite	WOCF (including baseline value)
Change in EQ-5D-5L index score from baseline to Weeks 1, 4, 8, 12, and 16	Continuous	Composite	WOCF (including baseline value)
Change in EQ-5D-5L visual analogue scale score from baseline to Weeks 1, 4, 8, 12, and 16	Continuous	Composite	WOCF (including baseline value)

Page 126 of 157

Endpoints	Type of endpoint	Primary estimand		
		Strategy to handle IEs	Handling of missing data and data collected after IE	
Change in WPAI:CHE absenteeism score from baseline to Week 4, 8, and 16 	Continuous	Composite	WOCF (including baseline value)	
Change in WPAI:CHE presenteeism score from baseline to Week 4, 8, and 16 	Continuous	Composite	WOCF (including baseline value)	
Change in WPAI:CHE work productivity loss score from baseline to Week 4, 8, and 16 	Continuous	Composite	WOCF (including baseline value)	
Change in WPAI:CHE activity impairment score from baseline to Week 4, 8, and 16	Continuous	Composite	WOCF (including baseline value)	

- 1) Among subjects with a baseline HESD itch score (weekly average) ≥4 points.
- 2) Among subjects with a baseline HESD itch score (weekly average)  $\geq 3$  points.
- 3) Among subjects with a baseline HESD score (weekly average) ≥4 points.
- 4) Among subjects with a baseline HESD score (weekly average) ≥3 points.
- 5) Among subjects with a baseline HESD pain score (weekly average) ≥4 points.
- 6) Among subjects with a baseline HESD pain score (weekly average) ≥3 points.
- 7) Among subjects with a baseline HEIS score  $\geq 1.5$  points.
- 8) Among subjects with a baseline HEIS PDAL score ≥1.5 points.
- 9) Among subjects with a baseline DLQI score ≥4 points.
- 10) Among subjects with paid work at baseline.

Abbreviations: DLQI = Dermatology Life Quality Index; HECSI = Hand Eczema Severity Index; HECSI-75 = at least 75% improvement in HECSI from baseline; HECSI-90 = at least 90% improvement in HECSI from baseline; HESD = Hand Eczema Symptom Diary; HEIS = Hand Eczema Impact Scale; IE = intercurrent event; IGA-CHE = Investigator's Global Assessment for chronic hand eczema; IGA-CHE TS = IGA-CHE treatment success, i.e. an IGA-CHE score of 0 (clear) or 1 (almost clear) with a ≥2 step improvement from baseline; IMP = investigational medicinal product; MAR = missing at random; MI = multiple imputation; PDAL = Proximal Daily Activity Limitations; WOCF = worst observation carried forward; WPAI:CHE = Work Productivity and Activity Impairment: Chronic Hand Eczema.

# 14.3.10 Analysis of patient-reported outcomes

The 3 PGI-S scores (Itch PGI-S, Pain PGI-S, and HESD PGI-S), the 3 PGI-C scores (Itch PGI-C, Pain PGI-C, and HESD PGI-C), and PaGA score will be summarised by visit for each treatment group.

# 14.3.11 Analysis of pharmacokinetics

Delgocitinib plasma concentration will be summarised for the safety analysis set by visit using geometric mean, coefficient of variation (derived based on a log-normal distribution assumption), median, 1st quartile, 3rd quartile, minimum, and maximum values.

Trial ID: LP0133-1402 Date: 20-Aug-2021

Version: 4.0, Final Page 127 of 157

# 14.3.12 Analysis of safety

The analysis of safety will be based on the safety analysis set.

#### **14.3.12.1** Adverse events

AEs will be coded during the course of the trial according to Medical Dictionary for Regulatory Activities (MedDRA). AEs will be presented by preferred term and primary system organ class (SOC).

Treatment-emergent AEs will be summarised; however, all AEs recorded during the course of the trial will be included in subject data listings. An event will be considered treatment emergent if started after the first application of IMP or if started before the first application of IMP and worsened in severity after first dose of IMP. The tabulations described in the following will only include the treatment-emergent AEs. In each of the tabulations, AEs are defined by MedDRA preferred terms within primary SOC.

AEs will be summarised in terms of the number of subjects with at least 1 event, the percentage of subjects with at least 1 event, the number of events, and the event rate per 100 person years of observation time.

Related AEs are defined as AEs for which the investigator has not described the causal relationship to IMP as 'not related'.

An overall summary presenting any treatment-emergent AEs, deaths, SAEs, permanent discontinuations from IMP and/or withdrawals from the trial due to AEs, treatment-related AEs, and severe AEs will be presented.

Tabulations by SOC and preferred term will be presented for all AEs, SAEs, related AEs, AESIs, AEs leading to withdrawal from trial, and AEs leading to permanent discontinuation of IMP. In addition, all AEs will be presented by severity and causal relationship to IMP, respectively. If an AE worsens in severity, the severity will be reported as the most severe recording for that AE.

SAEs will be evaluated separately and a narrative will be given.

AESIs will be listed by treatment group. No narratives will be given.

AEs leading to withdrawal from trial or permanent discontinuation of IMP will be listed. The detailed listing will provide an overview of the individual cases and include the age and sex of

Page 128 of 157

the subject, treatment received at the time of AE onset, the AE preferred and reported terms, causality and severity of the AE, the action taken with the IMP, AE outcome, start and stop date of AE, duration of AE, and number of days since first and last IMP administration. No narratives will be given.

Other events (medication error, misuse, and abuse of IMP) will be tabulated and listed. No narratives will be given.

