Abbreviations: CHE = chronic hand eczema; COVID-19 = coronavirus disease 2019; DLQI = Dermatology Life Quality Index; HECSI = Hand Eczema Severity Index; HECSI-75 = at least 75% improvement in HECSI score from baseline; HECSI-90 = at least 90% improvement in HECSI score from baseline; HEIS = Hand Eczema Impact Scale; HESD = Hand Eczema Symptom Diary; IE = intercurrent event; IGA-CHE = Investigator's Global Assessment for chronic hand eczema; IGA-CHE TS = IGA-CHE treatment success, i.e. an IGA-CHE score of 0 (clear) or 1 (almost clear) with a ≥2 step improvement from baseline; IMP = investigational medicinal product; PDAL = Proximal Daily Activity Limitations.

Trial ID: LP0133-1402 Date: 20-Aug-2021

Page 42 of 157

Version: 4.0, Final

Panel 4: Secondary and exploratory objectives and endpoints

Objectives	Endpoints
Secondary objective	Secondary endpoint
To evaluate the safety of twice-daily applications of delgocitinib cream 20 mg/g compared with cream vehicle in the treatment of adult subjects with moderate to severe CHE.	Number of treatment-emergent  AEs from baseline up to Week 16 (Week 18 for subjects not participating in the LTE trial) per subject.
Exploratory objectives	Exploratory endpoints

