#### **Treatment period (Week 0 to Week 16)**

At baseline (Day 1), the subjects' eligibility to enter the trial will be confirmed. Eligible subjects will be randomised 2:1 to either delgocitinib cream 20 mg/g or cream vehicle.

Subjects will apply the IMP (delgocitinib cream 20 mg/g or cream vehicle) twice daily for 16 weeks. The first application of IMP will occur at the trial site on Day 1 after all baseline

Page 45 of 157

assessments have been carried out. All subsequent IMP applications will be performed by the subjects at home.

During the 16-week treatment period, subjects will return to the trial sites for efficacy and safety assessments at the visits outlined in Section 4. The last IMP application will occur at the subject's home before the subject attends the visit scheduled at Week 16. Efficacy and safety assessments during the treatment period will be performed as described in the schedule of trial procedures (Section 4).

At the Week 12 visit, subjects may be invited to participate in the LTE trial. For subjects who continue to the LTE trial, the following visits will (ideally) coincide to facilitate a seamless transition between the trials and continuous treatment with IMP (if applicable):

- The Week 12 visit in the present trial will ideally coincide with the screening visit in the LTE trial.
- The Week 16 visit in the present trial will coincide with the baseline visit in the LTE trial. Subjects must complete the 16-week treatment period (i.e. must not permanently discontinue IMP prior to Week 16) and the Week 16 visit in the present trial to be eligible for the LTE trial.

All eligible subjects who do not permanently discontinue IMP prior to Week 16 will be invited to participate in the LTE trial.

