#### 9.5 Rescue treatment

If medically necessary (i.e. to control intolerable CHE symptoms), rescue treatment for CHE may be prescribed to trial subjects at the discretion of the investigator. The investigators should make every attempt to conduct efficacy and safety assessments (e.g. disease severity scores, safety laboratory assessments) immediately before administering any rescue treatment. If rescue treatment is initiated, the subject must stop treatment with IMP immediately and will not be allowed to restart treatment with IMP. Subjects who discontinue IMP will be asked to attend an early termination visit, a follow-up visit (performed via phone, but can be a site visit if needed) 2 weeks after the last application of IMP, and also the primary endpoint visit at Week 16 (see Section 10.3 for details).

Page 55 of 157

Rescue treatment is defined as treatment initiated to treat intolerable CHE symptoms during the treatment and follow-up periods. It will be recorded in the eCRF if a medication is given as rescue treatment.

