# 13.2 Collection of adverse event reports

AE data must be collected from time of first trial-related activity after the subject has signed the ICF until end of trial (as defined in Section 7.3).

AEs must be assessed by a physician.

At all visits, the subject will be asked a non-leading question by the investigator about AEs, e.g.: 'How have you felt since I saw you last?'. Subject-reported local tolerability will be queried specifically (see Section 11.5.5) and reported as AE(s) if deemed relevant by the investigator. In case of suspected local skin reaction related to IMP application, the final diagnosis based on the IMP patch test result (see Section 11.5.5.1) must be recorded as an AE. If the AE qualifies as an SAE, expedited reporting is required (Section 13.4). It is important that the investigator also observes the subject for any changes not reported by the subject and records these changes.

To avoid duplicate reporting of AEs in the present trial and the LTE trial, any AE with onset before the baseline visit in the LTE trial should be recorded as an AE in the present trial. If ongoing at the screening or baseline visit in the LTE trial, the AE should also be recorded as medical history in the LTE trial. An AE with onset after the baseline visit in the LTE trial should be recorded as an AE in the LTE trial.

Refer to Sections 11.5.1 to 11.5.5 for principles for data entry in the eCRF.

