## 13.7 Follow-up for final outcome of adverse events

During the trial, the investigator should follow up for final outcome on all AEs (including SAEs) until the subject's last visit in the trial. For subjects completing the treatment period and not participating in the LTE trial, this will be the safety follow-up visit. For subjects prematurely discontinuing IMP prior to Week 16, the last visit will in most cases be the primary endpoint visit. For subjects who will participate in the LTE trial, the investigator should follow up on the outcome of all non-serious AEs classified as possibly or probably related to the IMP for 14 days after end of treatment in the present trial, or until the final outcome is determined, whichever comes first. This could be at a safety follow-up visit via phone or at an LTE trial site visit. Non-serious AEs classified as not related to the IMP do not need to be followed up for the final outcome.

All SAEs must be followed up until a final outcome has been established, that is, the follow-up may continue beyond the end of the clinical trial. For SAEs which have stabilised and from which the subject cannot be expected to recover during the trial or the safety follow-up period, e.g. chronic or stabilised conditions, the final outcome at the investigator's discretion should be reported as 'recovering/resolving' or 'not recovered/not resolved'. In addition, a statement detailing why the subject cannot be expected to recover during the trial, e.g. that the SAE has stabilised or is chronic, should be added to the narrative description of the SAE on the SAE form.

Any pregnancy occurring during the trial will be followed up as described in Section 13.5.1.

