# 14.3.2 Disposition of subjects

The reasons for permanent discontinuation of IMP and for not completing the trial will be presented for all randomised subjects and by treatment group.

An overall summary of subject disposition will be presented for all randomised subjects. The disposition summary will include information on the number of randomised, exposed, included in the FAS, permanently discontinuing IMP, and not completing the trial by treatment group and overall.

Trial ID: LP0133-1402 Date: 20-Aug-2021

Version: 4.0, Final Page 102 of 157

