# 14.3.4 Exposure and treatment compliance

The duration of exposure to treatment in a specific week interval will be calculated as the number of days from date of first application of IMP in that period to the date of last application of IMP in that period, both days included.

Exposure to treatment will be presented for the safety analysis set as days of exposure per treatment group.

The average weekly and total amount of IMP used will be presented for the safety analysis set by treatment group for each visit interval and for the total treatment period.

Treatment compliance will be presented for the safety analysis set for each treatment group.

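### AE tables do not separate onset on IMP from onset after IMP or rescue, and the per-subject AE count runs longer for completers who do not join the LTE trial

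*Combined protocol and SAP*

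**What the plan says.** **Definition.** Section 14.3.12.1 states: "An event will be considered treatment emergent if started after the first application of IMP"; an event that began earlier but became more severe after the first dose also counts. The synopsis and Panel 4 (Section 6) carry the same rule. None of the three gives an end point tied to the last application. The AE tables are limited to treatment-emergent events, and their rates use observation time as the denominator.

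**Collection.** Section 13.2: "AE data must be collected from time of first trial-related activity after the subject has signed the ICF until end of trial". Subjects who stop IMP early are asked to return at Week 16 (Sections 4 and 10.3), and Panel 2 schedules AE collection at that visit. Section 13.7: "For subjects prematurely discontinuing IMP prior to Week 16, the last visit will in most cases be the primary endpoint visit".

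**Rescue.** Section 9.5: "If rescue treatment is initiated, the subject must stop treatment with IMP immediately", with no restart. Section 9.7 allows otherwise prohibited medication as rescue; Panel 7 lists systemic immunosuppressants, retinoids and corticosteroids among the prohibited drugs.

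**Per-subject count.** The secondary safety endpoint in Panel 4 is the number of treatment-emergent "AEs from baseline up to Week 16 (Week 18 for subjects not participating in the LTE trial) per subject". Section 7.1 on LTE entry: "All eligible subjects who do not permanently discontinue IMP prior to Week 16 will be invited to participate in the LTE trial".

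**The concern.** An AE that starts weeks after the last application, possibly on a systemic rescue drug, enters the same arm-level table as an AE that starts during daily use of the cream. No planned table marks the difference. This covers the AESI tables too (eczema herpeticum, deep vein thrombosis, pulmonary embolism; Section 13.6.1), where the placement of one or two events can change how a small table reads.

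The count of treatment-emergent AEs per subject is the only named safety endpoint. Its window depends on whether the subject joins the LTE trial, which is decided after randomisation and is open only to subjects still on IMP at Week 16. If joining differs between arms, so does average counting time.

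At stake is how the safety profile is read: how many AEs arose on IMP, after IMP, or after rescue.

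**Working it through.** The documents give no stopping rate, LTE-entry rate or AE rate, so there is no figure of the plan's own to reproduce. The timings come from the protocol; every rate below is an assumption.

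**Inputs from the documents.** Planned treatment of 16 weeks; primary endpoint visit 112 days after baseline (Section 4, footnote 5); follow-up 2 weeks after last application (Sections 7.1 and 10.3); 450 subjects randomised 2:1 (Section 14.1), so 300 and 150.

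**One early stopper who returns at Week 16.** Off-IMP days = 112 − 7 × week of stopping; subtract 14 for days beyond the follow-up interval.

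| Stops at | Off-IMP days | Beyond 14 days |
|---|---|---|
| Week 4 | 84 | 70 |
| Week 8 | 56 | 42 |
| Week 12 | 28 | 14 |

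**Off-IMP time by arm.** Assume stopping time T is uniform over 16 weeks. Mean weeks per stopper, w:
- from last dose: E[16 − T] = 8;
- beyond last dose + 14 days: E[max(14 − T, 0)] = 14²/(2 × 16) = 6.125.

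With stopping rate d and share s of stoppers who stay to Week 16, the share of planned time is d × s × w/16. At d = 8%/20% (delgocitinib/vehicle):

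| s | Beyond last dose + 14 days | From last dose |
|---|---|---|
| 25% | 0.8% / 1.9% | 1.0% / 2.5% |
| 50% | 1.5% / 3.8% | 2.0% / 5.0% |
| 100% | 3.1% / 7.7% | 4.0% / 10.0% |

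In subjects, 8% of 300 is 24 and 20% of 150 is 30. With s = 100% that is 24 × 6.125 = 147 and 30 × 6.125 = 184 subject-weeks beyond 14 days, or 24 × 8 = 192 and 30 × 8 = 240 from last dose, out of 300 × 16 = 4,800 and 150 × 16 = 2,400 planned.

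**Effect on the rate ratio.** Let the true on-IMP ratio be 1 and the off-IMP AE rate be k times the on-IMP rate, with k from 0.5 to 2. Per subject, on-time = 16(1 − d) + d(16 − w) and off-time = d × s × w. Arm rate = (on + k × off)/(on + off).

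Example with w = 6.125, s = 100%, k = 2. Off-time is 0.08 × 6.125 = 0.49 and 0.20 × 6.125 = 1.225. The rates are (15.51 + 0.98)/16 = 1.031 and (14.775 + 2.45)/16 = 1.077, so the ratio is 0.957. With k = 0.5 it is 0.985/0.962 = 1.024.

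| Scenario | Ratio, k = 2 to k = 0.5 |
|---|---|
| 8%/20%, s = 100%, w = 6.125 | 0.957 to 1.024 |
| 8%/20%, s = 50%, w = 6.125 | 0.977 to 1.012 |
| 8%/20%, s = 25%, w = 6.125 | 0.988 to 1.006 |
| 8%/20%, s = 100%, w = 8 | 0.945 to 1.032 |
| 5%/30%, s = 100%, w = 6.125 | 0.914 to 1.051 |
| 5%/30%, s = 100%, w = 8 | 0.891 to 1.068 |

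**LTE window among completers.** The longer window is 18/16 = 1.125 times the shorter. If 90% of delgocitinib and 70% of vehicle completers join, mean counting time is 16 × 0.9 + 18 × 0.1 = 16.2 weeks against 16 × 0.7 + 18 × 0.3 = 16.6. At equal AE rates the count ratio is 16.2/16.6 = 0.976, or 1.025 if the arms are reversed. With equal joining it is 1.

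**The case against.** The case against is substantial, and much of it stands.

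- **Causality tables.** A reader might infer that these ignore timing. Appendix 2 does not support that: temporal sequence is a criterion at every level, and the probable category adds improvement on stopping. The tables remain an investigator's judgement rather than a split by date.
- **Listing of AEs leading to withdrawal or IMP discontinuation.** It shows treatment at onset and days since last IMP. This helps, but only for a subset. An AE that starts after IMP has stopped cannot have caused the stop, so the listing largely misses the events in question.
- **Exposure and disposition.** Section 14.3.4: "Exposure to treatment will be presented for the safety analysis set as days of exposure per treatment group". Section 14.3.2: "The reasons for permanent discontinuation of IMP and for not completing the trial will be presented for all randomised subjects and by treatment group". Together they let a reader gauge off-IMP time by arm, but not which AEs fell in it.
- **Person-year rates.** They adjust for length of observation, including the 16/18-week difference, but not for treatment state.
- **Other safety outputs.** A reader might infer that the whole safety analysis is mixed. It is not: local tolerability, laboratory tests, vital signs and ECG are not scheduled at the primary endpoint visit. The gap is confined to tables built from the AE form.
- **Week 18.** A reader might infer that everyone outside the LTE trial is counted for two more weeks. Early stoppers cannot join, yet Section 13.7 has their last visit at Week 16 in most cases, and their follow-up visit can fall before Week 18 (Section 4, footnote 4). The real difference mainly concerns completers who do not join.
- **Later SAP.** Section 14.3.14 says an SAP will be finalised before the code is broken. It is not among the documents and may already contain the split.

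**Conclusion.** The point holds as a gap in reporting, as the protocol is written. The AE-form tables combine events starting on IMP, after IMP and after rescue, and no planned table separates them. The per-subject count has unequal windows among completers according to a choice made after randomisation.

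The effect is probably small and could go either way. At an assumed 8%/20% stopping with all stoppers staying, a true ratio of 1 appears as 0.96 to 1.02 when time beyond last dose + 14 days counts as off-IMP, or 0.95 to 1.03 counting from last dose. It is closer to 1 if fewer stay, and reaches 0.89 to 1.07 only in the extreme 5%/30% case. These figures rest on assumed stopping, staying and off-IMP AE rates and on uniform stopping times.

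A reader might infer that the planned tables are wrong, or that they favour one arm. The documents support neither. Counting every event regardless of discontinuation or rescue is a legitimate view, and the direction depends on rates that nobody knows in advance. Section 14.3.12 plans no safety test, and the confirmatory procedure in Section 14.3.5 covers only the primary and key secondary endpoints. The point is therefore worth considering as a cheap improvement and does not threaten a conclusion.

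**What to change.** Keep the full-window tables and label them as counting AEs regardless of IMP discontinuation or rescue. Add the following to Section 14.3.12.1, or to the SAP finalised before unblinding if it is not already there:

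- **(a)** AE counts and rates, AESIs included, with matching person-time and split by onset: first to last IMP application; after last application without rescue; after start of rescue. If a lag after the last application is wanted, show it as its own row, so that on-IMP events stay separate, and state it as an analysis convention. The protocol's 14 days is a visit interval, not an established attribution window.
- **(b)** The per-subject treatment-emergent AE count with a common Week 16 cut-off for all subjects, beside the planned Week 16/18 count so that follow-up events are not lost.

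The cost is a few extra tables and no new data: last application date (Section 11.8), rescue flag and start date (Section 9.6) and AE dates (Section 13.3) are already collected. The downside is that the on-IMP view cuts follow-up at an event related to outcome, so it supplements the full-window view and does not replace it.
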